1.1. Synopsis

Protocol Title:

A Multicenter, Randomized, Double-Blind, Placebo-Controlled, Phase 2a Clinical Study to Evaluate the Safety, Efficacy, Pharmacokinetics, and Pharmacodynamics of Orally Administered TERN-501 as Monotherapy as well as in Combination with TERN-101 in Noncirrhotic Adults with Presumed Non-Alcoholic Steatohepatitis (NASH)

Rationale:

Due to the multifactorial pathophysiology of NASH, including metabolic dysregulation, increased hepatic oxidative stress and inflammation, and the onset of profibrogenic processes (Magee 2016), a combination approach to treatment with complementary mechanisms may be more efficacious than monotherapy. FXR activation has been shown to improve histological features associated with NASH including hepatic steatosis, inflammation, hepatocyte ballooning, and, in a phase 3 study, fibrosis (Younossi 2019).

Objectives and Endpoints:

Primary Objective	Primary Endpoint					
• To evaluate the effect of TERN-501 monotherapy on liver fat content as assessed by MRI-PDFF compared to placebo	 Relative change from baseline in MRI-PDFF at Week 12 for TERN-501 compared to placebo 					
Secondary Objectives	Secondary Endpoints					
 To evaluate the effect of TERN-501 monotherapy on cT1 relaxation time compared to placebo To evaluate the effect of TERN-501+TERN- 101 on liver fat content as assessed by MRI- PDFF and on cT1 relaxation time compared to placebo 	 Change from baseline in cT1 relaxation time at Week 12 for TERN-501 compared to placebo Relative change from baseline in MRI-PDFF at Week 12 for TERN-501+TERN-101 compared to placebo Change from baseline in cT1 relaxation time at Week 12 for TERN-501+TERN-101 compared to placebo 					
 To evaluate safety and tolerability of TERN- 	Patient incidence of treatment emergent					
501 monotherapy and TERN-501+TERN-101	adverse events					
Exploratory Objectives	Exploratory Endpoints					
 To explore the effect of TERN-501 monotherapy on efficacy and markers of target engagement compared to placebo To explore the effect of TERN-501+TERN- 101 on efficacy and markers of target engagement, compared to placebo and/or each monotherapy 	 Change from baseline in the following parameters, as applicable: ALT, AST, and GGT FIB-4, CK-18 (M30 and M65), ELF (PIIINP, TIMP-1, HA), PRO-C3, and FAST score TE and CAP MRI-PDFF (relative change) and cT1 SHBG Lipid panel (for PD as well as safety evaluation) rT3 					
	\circ FGF19, bile acids, and 7α C4					
	• Proportion of responders on MRI-PDFF and/or cT1 with the following:					

	$ \circ \geq 30\% \text{ relative reduction in MRI-PDFF} \circ \geq 80 \text{ msec reduction in cT1} $
 To evaluate the pharmacokinetics of TERN-501 and TERN-101 administered alone and in combination 	• PK parameters (e.g., AUC, C _{max} , C _{tau})

Abbreviations: $7\alpha C4 = 7\alpha$ -hydroxy-4-cholesten-3-one; ALT = alanine transaminase; AST = aspartate transaminase; AUC = area under the concentration-time curve, CAP = controlled attenuation parameter; CK-18 = cytokeratin-18; C_{max} = maximum observed concentration; cT1 = corrected T1; C_{tau} = concentration at the end of the dosing interval; ELF = enhanced liver fibrosis; FAST score = FibroScan AST score; FGF19 = fibroblast growth factor-19; FIB-4 = fibrosis-4; GGT = gamma-glutamyl transferase; HA = hyaluronic acid; MRI = magnetic resonance imaging; MRI-PDFF = magnetic resonance imaging proton density fact fraction; PIIINP = procollagen III N-terminal propeptide; PD = pharmacodynamics; PK = pharmacokinetics; PRO-C3 = released N-terminal pro-peptide of type III collagen; rT3 = reverse T3; SHBG = sex hormone binding globulin; TIMP-1 = tissue inhibitor of metalloproteinases-1; TE = transient elastography

Overall Design:

This study is a multicenter, randomized, double-blind, placebo-controlled, parallel-group treatment, phase 2a study.

Approximately 140 noncirrhotic NASH patients with fibrosis identified based on prior liver biopsy and/or imaging and clinical criteria who meet study eligibility criteria will be enrolled and randomized into one of the 7 treatment groups: once daily orally administered TERN-501 1 mg (n=20), TERN-501 3 mg (n=20), TERN-501 6 mg (n=20), TERN-501 3 mg+TERN-101 10 mg (n=20), TERN-501 6 mg+TERN-101 10 mg (n=20), or matching placebo (n=20).

Of the 140 patients randomized, approximately 42 patients (approximately 6 per group) will take part in an intensive PK and pharmacodynamic (PD) collection after the first dose and after the last dose of study drug. Patients who are not participating in the PK/PD sub-study will have sparse PK and trough PD sampling.

Number of Patients:

Approximately 140 patients will be randomly assigned to one of the 7 treatment groups specified above.

Patients who are randomized but do not receive study drug for any reason may be replaced. In addition, patients who discontinue treatment early for reasons other than safety (i.e., withdrawal of consent, lost to follow-up, patient relocated, etc.) may also be replaced, at the Sponsor's discretion. Replacement patients will receive the same treatment assignment as the patient that discontinued treatment early.

Study Centers Planned:

Approximately 40 centers in the United States

Intervention Groups and Duration:

The total study duration will be approximately 22 weeks, consisting of up to a 6-week Screening period (42 days), a 12-week Treatment period, and a 4-week Follow-up period.

Screening Period

The \leq 6-week Screening period initiates upon signing an Informed Consent, at which point eligibility criteria will be reviewed. Each eligible patient will be scheduled for Week 0/Day 1.

Treatment Period

The 12-week double-blind, randomized treatment period will initiate at Week 0/Day 1 after confirming eligibility. The blinded study drugs (TERN-501, TERN-101, TERN-501+TERN-101, or matching placebo) will be orally administered once daily.

Patients will return to the site at Weeks 2, 4, 6, 8, and 12 for safety and laboratory assessments. Study drug will be dispensed at Week 0/Day 1, Week 4, and Week 8. Week 12 is the last day of treatment.

Intensive PK/PD sampling will be performed in approximately 42 patients participating in the PK/PD sub-study on the day of first dose (Week 0/Day 1) and on the day of last dose of study drug (Week 12).

Transient elastography (TE) and controlled attenuation parameter (CAP) by FibroScan[®] will be completed at Screening or Day 1, and Week 12. MRI-PDFF, and cT1 will be completed at Screening, Week 6, and Week 12. FibroScan[®] and MRI-PDFF will be performed at early termination (ET) only if not done within the prior 4 weeks, and the patient has had at least 4 weeks of dosing.

[figure not shown]
All visits through Week 12 will have $a \pm 3$ days visit window from the specific study day.

Follow-up Period

All patients will return to site for follow up safety assessments at Week 16. Week 16 will have a -7 days /+2 days visit window.

If study drug is permanently discontinued for any reason outlined in Section 7, the patient will be encouraged to remain in the study to be evaluated at the remaining visits through the Follow-Up visit. See the Schedule of Activities for data to be collected at the time of discontinuation of study drug and follow-up, and for any further evaluations that need to be completed.

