9.1. Statistical Hypotheses

The primary statistical analysis will test whether the mean relative change from baseline in MRI-PDFF is (H₁) or is not (H₀) different between placebo and TERN-501 monotherapy. Secondary statistical analyses will test whether the mean relative change from baseline in MRI-PDFF is (H₁) or is not (H₀) different between placebo and TERN-501+TERN-101. Similarly, statistical analyses of cT1 will test whether the mean change from baseline is (H₁) or is not (H₀) different between placebo and TERN-501 monotherapy and between placebo and TERN-501+TERN-101. In addition, exploratory analyses will evaluate all pairwise comparisons between the different TERN-501 doses and of TERN-101 compared to placebo and will be considered nominal and descriptive.

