9.2. Sample Size Determination

Approximately 140 patients will be randomized into one of the 7 groups (n=20 each) to detect a clinically meaningful difference in the primary endpoint and secondary endpoints of MRI-PDFF relative reduction at Week 12 and secondary endpoints of cT1 reduction at Week 12 between placebo and TERN-501 monotherapy and separately between placebo and TERN-501+TERN-101.

Power was estimated based on published literature for THR- β agonist resmetirom (to estimate TERN-501 effect) and clinical data for TERN-101 (Study TERN101-2001). Assuming a pooled standard deviation of 22% (Study TERN101-2001 final analysis), with a two-sided alpha of 0.05, a mean relative reduction difference in MRI-PDFF at Week 12 of

- 23% between placebo (n=20) and TERN-501 monotherapy (n=20) will provide approximately 90% power (Harrison 2019).
- 36% between placebo (n=20) and TERN-501+TERN-101 (n=20) will provide >90% power, based on placebo treatment effect from resmetirom (Harrison 2019) and sum of treatment effects from resmetirom (to estimate TERN-501 effect) and minimum treatment effect for TERN-101 (Study TERN101-2001), assuming an additive effect of the two agents in combination.

Assuming a pooled standard deviation of 82 msec (Study TERN101-2001 final analysis), with a two-sided alpha of 0.05, a mean reduction difference in cT1 at Week 12

- of 77 msec between placebo (n=20) and TERN-501 monotherapy (n=20) will provide approximately 82% power (Harrison 2018).
- 134 msec between placebo (n=20) and TERN-501+TERN-101 (n=20) will provide >90% power, based on placebo treatment effect from resmetirom (Harrison 2019) and sum of treatment effects from resmetirom (to estimate TERN-501 effect) and minimum treatment effect for TERN-101 (Study TERN101-2001), assuming an additive effect of the two agents in combination.

Patients who are randomized but do not receive study drug for any reason may be replaced. In addition, patients who discontinue treatment early for reasons other than safety (i.e., withdrawal

Protocol TERNCB-2002 Terns, Inc.

of consent, lost to follow-up, patient relocated, etc.) may also be replaced, at the Sponsor's discretion. Replacement patients will receive the same treatment assignment as the patient that discontinued treatment early.

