9.4.4. Exploratory Endpoints

9.4.4.1. Efficacy Endpoints

All exploratory efficacy analyses will be performed on Efficacy Analysis Set. Exploratory analyses will evaluate all pairwise comparisons between the 7 treatment groups and will be considered nominal and descriptive.

The primary and secondary endpoints evaluate Week 12 MRI-PDFF and cT1, while exploratory endpoints will summarize and analyze other applicable time points and additional treatment group comparisons of TERN-501+TERN-101 to TERN-501 monotherapy and TERN-101 monotherapy in the same manner specified for the primary and secondary endpoints. Additional details will be specified in the SAP.

Change (and separately percent change) from baseline in liver enzymes, NASH and fibrosis biomarkers, and liver stiffness will be summarized and analyzed at applicable time points using the same ANCOVA model specified for the primary endpoint.

FAST score will be calculated based on liver stiffness and AST values (Newsome 2020).

MRI-PDFF responders will be defined as any patient with a relative decrease of at least 30%. Non-responders will be defined as any patient who did not have at least a 30% relative decrease. The number and percentage, with associated two-sided exact (Clopper-Pearson) 95% CI, of patients in each category (response, nonresponse) will be presented by treatment group at applicable time points. A Chi-square test will be used to compare treatment groups.

cT1 responders will be defined any patient with a decrease of at least 80 msec. Non-responders will be defined any patient who did not have at least an 80 msec decrease. cT1 response will be summarized and analyzed at applicable time points in the same manner as specified for MRI-PDFF.

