2.1.4. Treatment Assignment, Blinding, and Randomization Methodology

Patients will be randomized to study drug or placebo using an Interactive Web Response System (IWRS). Approximately 140 patients will be randomized at an overall ratio of 1:1:1:1:1:1:1 into the 7 groups treatment groups as described in Table 2.

Investigators, patients, all study personnel, and the Sponsor will remain blinded to each patient's assigned dose group throughout the course of the study. The randomization codes will be provided to bioanalytics to allow for the exclusion of placebo patients from the PK assay.

Randomization codes will remain blinded until the trial is officially unblinded.

Emergency unblinding procedures are outlined in Section 6.4.1 of the study protocol and in the unblinding plan. Additional unblinding will be reviewed in the medical monitor plan (Maintaining Study Blind and Unblinding Plan).

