7.6. Multiple Comparisons/Multiplicity

Table 6 depicts the pairwise comparisons which will be performed denoted by "X".

Table 6 Pairwise Comparison for Display

	101	501 (1)	501 (3)	501 (6)	101+501 (3)	101+501 (6)
Placebo	X	X	X	X	X	X
501 (3)					X	
501 (6)						X

Table 7 depicts the order or comparison for the hierarchical testing strategy.

Statistical Analysis Plan CONFIDENTIAL Labcorp Drug Development Study: 000000231152 Protocol Reference: TERNCB-2002

Table 7 Hierarchical Testing Strategy

MRI-PDFF						
	101	501 (1)	501 (3)	501 (6)	101+501 (3)	101+501 (6)
Placebo		3	2	1	5	4
501 (3)					7	
501 (6)						6
cT1						
	101	501 (1)	501 (3)	501 (6)	101+501 (3)	101+501 (6)
Placebo	4	3	2	1	6	5
501 (3)					8	
501 (6)						7

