8.5. Electrocardiograms

Summary statistics will be provided for heart rate, PR interval, QRS interval, QT interval, and QTcF at each visit. The investigator interpretation is collected as normal, abnormal not clinically significant (NCS), or abnormal clinically significant (CS). Patients whose interpretation shifts from normal to abnormal (CS or NCS) will be listed separately including description of the abnormality and any associated comments.

Categorical summaries will for baseline, worst post-baseline, and change from baseline for the following QTcF values will be presented:

- > 450 msec
- > 480 msec
- > 500 msec
- Change from baseline > 30 msec
- Change from baseline > 60 msec

CONFIDENTIAL

All ECG results will be presented in by-patient data listings. If applicable, cardiologist consult information will be presented in a separate by-patient data listing.

CONFIDENTIAL

9. Other Assessments

Other assessments will be provided in by-patient data listings only; no summary tables will be provided, including but not limited to the following:

- Eligibility details including unmet eligibility criteria
- Informed consent
- Randomization schema
- Physical examination collection information
- Serology
- Pregnancy testing
- FSH test
- Urine drug screen
- Alcohol test
- Urinalysis and Urine Microscopic Examination
- Coagulation
- Hemoglobin A1c
- Direct bilirubin
- Indirect bilirubin
- Laboratory reference ranges
- Cardiology consult
- Overdose
- Comments

Final, Version 2.0, 26JULY2023

CONFIDENTIAL

10. Changes to Protocol Planned Analyses

There were no changes from the protocol planned analyses.

CONFIDENTIAL

Statistical Analysis Plan CONFIDENTIAL Labcorp Drug Development Study: 000000231152 Protocol Reference: TERNCB-2002

11. Appendices

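### The protocol plans pairwise comparisons among all seven groups, but SAP Table 6 omits every comparison between two TERN-501 doses, and SAP Section 10 declares no change

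*Protocol*

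**What the plan says.** Protocol 1.1 and 4.1 set out seven equal arms: placebo, TERN-101 10 mg, TERN-501 at 1, 3 and 6 mg, and TERN-501 at 3 and 6 mg each with TERN-101 10 mg. The synopsis gives the monotherapy arms as "once daily orally administered TERN-501 1 mg (n=20), TERN-501 3 mg (n=20), TERN-501 6 mg (n=20" per arm). SAP 2.1.4 confirms the allocation: "Approximately 140 patients will be randomized at an overall ratio of 1:1:1:1:1:1:1 into the 7 groups treatment groups".

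Protocol 9.4.4.1 says "Exploratory analyses will evaluate all pairwise comparisons between the 7 treatment groups" and calls these nominal and descriptive. It also names comparisons of the combination with each monotherapy, TERN-101 included, and leaves further detail to the SAP. Protocol 9.1 says "exploratory analyses will evaluate all pairwise comparisons between the different TERN-501 doses". That sentence continues with TERN-101 and placebo, and could be read as comparisons with placebo only, so 9.4.4.1 is the clear statement.

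SAP 7.6 says "Table 6 depicts the pairwise comparisons which will be performed denoted by" an X, and Table 6 marks eight cells: six groups against placebo, the 3 mg combination against 3 mg alone, and the 6 mg combination against 6 mg alone. SAP 7.7 fits an ANCOVA with treatment group and baseline, reports an LS mean, SE and 95% CI for every arm, and takes its between-group comparisons from Table 6. SAP Section 10 states: "There were no changes from the protocol planned analyses".

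**The concern.** The SAP narrows what the protocol promised and does not say so. The effect reaches well beyond one endpoint. MRI-PDFF, cT1, liver enzymes, fibrosis markers and scores, rT3, elastography, SHBG and LDL cholesterol are all analysed with the Section 7.6 pairs, so one table removes the dose comparison from all of them.

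Dose is an open question here. Protocol 4.3 describes the monotherapy arms as dose-ranging. The first-in-human data it cites point in two directions: SHBG rose 17%, 57% and 136% at 1, 3 and 6 mg, while LDL cholesterol fell 16.4%, 16.7% and 18.8%. Readers will want to know which pattern liver fat follows. Without a planned difference and interval they will tend to compare p-values against placebo. One dose passing 0.05 while another misses it is not evidence that the two differ.

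**Working it through.** **Counting the pairs.** Seven groups give 7 × 6 / 2 = 21 pairs. Table 6 marks 6 + 2 = 8, so 13 are omitted. Four of the 13 compare TERN-501 doses: 6 v 3, 6 v 1 and 3 v 1 mg as monotherapy, and the 6 mg v the 3 mg combination. Two more are each combination v TERN-101 alone, which protocol 9.4.4.1 names. The other seven are each TERN-501 monotherapy v TERN-101 (three) and combination v a different monotherapy dose (four).

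**Inputs.** From protocol 9.2: n = 20 per arm; SD 22 points for relative change in MRI-PDFF and 82 msec for cT1; two-sided alpha 0.05; assumed effects v placebo of 23 points and 77 msec.

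**The plan's own figures.** The plan states "23% between placebo (n=20) and TERN-501 monotherapy (n=20) will provide approximately 90% power". The SE of a difference is 22 × √(2/20) = 6.96, so the noncentrality is 23/6.96 = 3.31. Noncentral t with 38 df gives 89.6%, which agrees. For cT1, the SE is 82 × √(2/20) = 25.93 and 77/25.93 = 2.97, which gives 82.5% against the stated 82%. Both figures concern one dose against placebo only.

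**Precision of a between-dose difference.** In the seven-arm ANCOVA with one covariate, the residual df are 140 − 7 − 1 = 132 and t(0.975) = 1.978.
- MRI-PDFF half-width: 1.978 × 6.96 = 13.8 points.
- cT1 half-width: 1.978 × 25.93 = 51.3 msec.
- MRI-PDFF difference detectable with 80% power: about 20 points.

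**Power between doses.** The documents give no dose-response shape. I assume three rising shapes, each reaching 23 points at 6 mg: linear in dose, proportional to log(1 + dose), and Emax with an ED50 of 1.5 mg. The difference for doses a and b is 23 × [f(a) − f(b)] / f(6). For 6 v 3 mg on the log shape, for example, this is 23 × (1.946 − 1.386)/1.946 = 6.6. Power is from noncentral t, 132 df, with noncentrality equal to the difference divided by 6.96.

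| Shape | 6 v 3 mg: difference, power | 3 v 1 mg: difference, power | 6 v 1 mg: difference, power |
|---|---|---|---|
| Linear | 11.5, 38% | 7.7, 19% | 19.2, 78% |
| Log | 6.6, 16% | 8.2, 22% | 14.8, 56% |
| Emax | 3.8, 8% | 7.7, 19% | 11.5, 38% |

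Power for adjacent doses is 38% or less throughout. Only 6 v 1 mg, under a near-linear response, approaches conventional power. The calculation allows for no dropout and no gain from baseline adjustment.

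**The case against.** A reader might infer that the SAP gives no information on which dose does better. The documents do not support that. SAP 7.7 reports LS means, SEs and CIs by arm, and SAP 7.8 adds responder rates with exact intervals, so point differences are recoverable. Nor is dose order ignored: Table 7 tests 6 mg, then 3 mg, then 1 mg against placebo. The single ANCOVA also pools residual variance over all seven arms.

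Dose selection is not a stated objective. The efficacy objectives are against placebo or against each monotherapy, and the protocol itself calls the missing comparisons nominal. Power is also low enough that the added rows will seldom settle a choice between neighbouring doses. All of this stands and limits the weight of the point. It does not remove it. Protocol 9.4.4.1 leaves details to the SAP, but dropping 13 of 21 planned pairs is a change, and Section 10 says there was none. Low power is itself a reason to print the interval, because a wide CI shows how little support a ranking of doses has.

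It is also tempting to require a dose-trend contrast over placebo, 1, 3 and 6 mg. With centred log(1 + dose) scores of −1.01, −0.31, 0.38 and 0.94, such a contrast would be significant 55% of the time if all three doses had the same 15-point effect, and 89% of the time at 23 points. It tests mainly drug against placebo and cannot show that one dose beats another. Neither document plans a trend test, so I would not ask for one.

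**Conclusion.** The discrepancy is real. The protocol plans all 21 nominal pairs, the SAP performs 8 with none between TERN-501 doses, and SAP Section 10 declares no change. What is lost is the planned between-dose difference with its own SE and 95% CI, on MRI-PDFF, cT1 and every other endpoint that uses the Section 7.6 pairs. The primary comparisons with placebo and their stated power are unaffected.

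A restored MRI-PDFF comparison would carry a half-width of about 13.8 points (51 msec for cT1). That rests on the plan's SDs and 20 evaluable patients per arm; fewer at Week 12 would widen it. The between-dose power figures also rest on the three assumed shapes. The change should be made, because it restores a protocol commitment at almost no cost, but it will not by itself identify the best dose.

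**What to change.** 1. Add six pairs to SAP Table 6: 501(6) v 501(3), 501(6) v 501(1), 501(3) v 501(1), 101+501(6) v 101+501(3), 101+501(3) v 101, and 101+501(6) v 101.
2. Report each as an LS mean difference with SE and 95% CI from the Week 12 ANCOVA already specified in SAP 7.7, labelled nominal and kept outside the Table 7 hierarchy.
3. State beside them the expected half-widths of about 13.8 points and 51 msec, and that a non-significant difference does not show that two doses are equivalent.
4. Correct SAP Section 10. With the six additions Table 6 holds 14 of the 21 pairs; list the other seven as omitted from the protocol plan and give the reason.

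The cost is a few lines of SAP text and extra estimate statements in a model that is already being fitted. No patients, visits or alpha are added. The tables become longer and show more nominal comparisons, which is why the labelling matters.

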1.2. Schema

1.3. Schedule of Activities (SoA)

	Screening]	Freatmen	t Period ^f			Follow -Up ^b	ET ^a	Notes
Visit	Screening	Week 0	Week 2	Week 4	Week 6	Week 8	Week 12	Week 16		
Study Day		Day 1	15	29	43	57	85	113		
Schedule Window (days)	-42 days		± 3	± 3	± 3	± 3	± 3	-7 /+2		Patients discontinuing the study at any time for any reason (Early Termination) should complete the ET visit as soon as feasible and return for a Follow-Up visit 4 weeks (-7 days /+2 days) after the last dose of study drug.
Clinical Procedure	s/Assessmen	its								
Written Informed Consent	х									Written informed consent may be obtained via telephone in accordance with Section 10.1.2. Screening may be initiated via telephone to avoid a visit to the site, if the patient is disqualified based on medical history.
Demographics	Х									Includes age (year of birth), sex, race, and ethnicity.
Weight	Х	х			Х		X	х	х	
BMI	Х									
Height	Х									
Medical history	х									Medical history including details of illnesses, allergies, or procedures including liver biopsy, date(s) of onset, whether condition(s) is currently ongoing, medication history, including alcohol use
Complete Physical Examination	х							Х	х	

	Screening		1	Freatmen	t Period ^f			Follow -Up ^b	ET ^a	Notes
Visit	Screening	Week 0	Week 2	Week 4	Week 6	Week 8	Week 12	Week 16		
Study Day		Day 1	15	29	43	57	85	113		
Schedule Window (days)	-42 days		± 3	± 3	± 3	± 3	± 3	-7 /+2		Patients discontinuing the study at any time for any reason (Early Termination) should complete the ET visit as soon as feasible and return for a Follow-Up visit 4 weeks (-7 days /+2 days) after the last dose of study drug.
Targeted Physical Examination		X¢	х	х	x	x	x			A targeted physical examination will be conducted as needed, based on clinical judgement of the Investigator, to evaluate reported current or prior AEs, symptoms reported by the patient, or abnormal laboratory readouts.
Vital Signs	х	Xc	x	х	x	x	x	х	х	Includes temperature, pulse rate, respiratory rate, and blood pressure. Blood pressure and pulse measurements should be preceded by at least 5 minutes of rest for the patient in a quiet setting without distractions.
12-lead ECG	х	Xc	х	х	x	x	x	х	х	Participants will lie supine in a quiet setting without distractions for at least 10 minutes prior to 12-lead ECG collection.
Smoking status		Х					Х		Х	
AE Review		←						>		See Section 8.5 for additional details on AE and SAE reporting.
Pruritus Assessment		←====						→		Reported AEs consistent with pruritus will be assessed using the Pruritus Numerical Rating Scale (Appendix 8). See Section 8.5.6 for additional details.
Concomitant Medications Review		←						→		

	Screening	Treatment Period ^f							ET ^a	Notes
Visit	Screening	Week 0	Week 2	Week 4	Week 6	Week 8	Week 12	Week 16		
Study Day		Day 1	15	29	43	57	85	113		
Schedule Window (days)	-42 days		± 3	± 3	± 3	± 3	± 3	-7 /+2		Patients discontinuing the study at any time for any reason (Early Termination) should complete the ET visit as soon as feasible and return for a Follow-Up visit 4 weeks (-7 days /+2 days) after the last dose of study drug.
Lifestyle Counseling		←====						→		Guidance should be provided on key elements of a healthy lifestyle at each visit including diet, exercise, weight loss, and avoidance of alcohol per standard of care management for this patient population.
Imaging Assessmen	nts									
TE and CAP by FibroScan®	х	Xi					х		х	If TE and CAP by FibroScan [®] was performed at Screening, it does not need to be repeated at Day 1. TE and CAP by FibroScan [®] should be performed at ET only if not done within the prior 4 weeks, and the patient has had at least 4 weeks of dosing.
MRI-PDFF ^e	х				x		x		x	Screening MRI-PDFF and MRI-cT1 may proceed on the basis of the initial ALT and AST level at Screening, given all other eligibility criteria are met, but randomization should not occur prior to confirmation of ALT and AST stability, as necessary.
MRI-cT1°	х				х		х		х	MRI-PDFF and MRI-cT1 should be performed at ET only if not done within the prior 4 weeks, and the patient has had at least 4 weeks of dosing.
PK and PD Proced	ures/Assess	ments								
Sparse PK Sampling			Xc	Xď	Xc	Xc	Xc		х	Only one sample will be collected at each visit, see footnotes for timing. Patients discontinuing the study at any time for any reason will have one sample collected at the ET visit. Refer to Appendix 2 for additional detail.

	Screening]	Freatmen	t Period ^f			Follow -Up ^b	ET ^a	Notes
Visit	Screening	Week 0	Week 2	Week 4	Week 6	Week 8	Week 12	Week 16		
Study Day		Day 1	15	29	43	57	85	113		
Schedule Window (days)	-42 days		± 3	± 3	± 3	± 3	± 3	-7 /+2		Patients discontinuing the study at any time for any reason (Early Termination) should complete the ET visit as soon as feasible and return for a Follow-Up visit 4 weeks (-7 days /+2 days) after the last dose of study drug.
Trough PD Sampling ^c		X	х	Х	х		х		Х	Refer to Appendix 2 for additional detail.
NASH/ Fibrosis Biomarkers ^c		х			х		х		х	Includes CK-18 (M30 and M65), ELF (PIIINP, TIMP-1, HA), and PRO-C3.
Intensive PK Sampling (PK/PD sub-study only)		х					Xi			Intensive PK sampling will be performed pre-dose and 1, 2, 4, 6, and 24 hours post the first dose of study drug on Week 0/Day 1, and at pre-dose and 1, 2, 4, 6, 24, 48, and 72 hours post last dose of study drug at Week 12. Patients should be instructed to hold their dose of study drug until after pre- dose and after 24-hour PK samples are collected. Refer to Appendix 2 for additional detail.
Intensive PD Sampling (PK/PD sub-study Only)		х					Xj			7α C4 and FGF19 will be collected at matching timepoints to Intensive PK sampling (above) except at Week 12 when 7α C4 and FGF19 will not be collected at 48 and 72 hours post dose. Refer to Appendix 2 for additional detail.
Clinical Laborator	y Procedure	es/Assessn	nents							
Patient Fasting	х	х	х	х	х	х	х	х	х	Patients must be in fasted state for at least 8 hours prior to blood collection and treatment administration, where applicable.

	Screening]	Freatmen	t Period ^f			Follow -Up ^b ET ^a		Notes	
Visit	Screening	Week 0	Week 2	Week 4	Week 6	Week 8	Week 12	Week 16			
Study Day		Day 1	15	29	43	57	85	113			
Schedule Window (days)	-42 days		± 3	± 3	± 3	± 3	± 3	-7 /+2		Patients discontinuing the study at any time for any reason (Early Termination) should complete the ET visit as soon as feasible and return for a Follow-Up visit 4 weeks (-7 days /+2 days) after the last dose of study drug.	
Chemistry ^e	x	x	x	x	x	x	x	x	X	Specific analytes are listed in Appendix 1. ALT and AST stability may be evaluated prior to randomization per Section 5. Increased monitoring criteria for elevated ALT and/or AST above 2×Baseline or above 5×ULN, and elevated ALP above 3×ULN are outlined in Appendix 3. A standard lipid test will be collected as part of the clinical chemistry at Screening to confirm eligibility (Appendix 1). During study treatment, lipid parameters for PD assessments listed in Table 9 of Appendix 2 will be collected and results will be blinded. HDL will remain unblinded and will be collected as part of clinical chemistry at all visits. Refer to Appendix 5 for the eGFR formula, to be calculated by central lab.	
Hematology ^c	х	Х	х	Х	Х	Х	Х	Х	x	Specific analytes are listed in Appendix 1.	
Coagulation ^c	х	х								Specific analytes are listed in Appendix 1. PT/INR will be tested at Screening, Week 0, and if significant abnormal liver function is observed.	
Urinalysis ^c	х				Х			х	х	Specific analytes are listed in Appendix 1. Microscopic examination is required if blood or protein is abnormal.	
Urine Drug Screen ^c	Х	Х		Х		Х	Х	Х	x	Randomization may proceed at Week 0 provided exclusion criteria 29 and 30 are not met.	

	Screening		1	Freatmen	t Period ^f			Follow -Up ^b ET ^a		Notes	
Visit	Screening	Week 0	Week 2	Week 4	Week 6	Week 8	Week 12	Week 16			
Study Day		Day 1	15	29	43	57	85	113			
Schedule Window (days)	-42 days		± 3	± 3	± 3	± 3	± 3	-7 /+2		Patients discontinuing the study at any time for any reason (Early Termination) should complete the ET visit as soon as feasible and return for a Follow-Up visit 4 weeks (-7 days /+2 days) after the last dose of study drug.	
Thyroid Axis Testing ^c	х	х	х		х		х	х	х	All thyroid axis samples (including any repeat tests) should be collected in the morning at approximately the same time on each visit day. Specific analytes are listed in Appendix 1. Post-dose T4 and rT3 results will remain blinded as outlined in Section 8.1.9.1. Refer to Section 8.1.8 for additional detail on thyroid axis safety monitoring. TBG and rT3 will be analyzed only at Week 0/Day 1 and Week 12 or ET.	
Bone turnover markers ^c		Х					х	х	х	Includes sCTX and sPINP.	
Sex Hormone Panel ^c		Х					X	Х	х	Specific analytes are listed in Appendix 1.	
Serology	х									Includes HBsAg, anti-HCV and anti-HIV.	
COVID-19 Assessment ^{c,g}	х	Х			х		х			Screening and on study COVID-19 assessments should be conducted in accordance with Appendix 9.	
Serum pregnancy test ^c	Х	Х		х		х	х		х	WOCBP only.	
Urine pregnancy test ^c		х								WOCBP only. Urine pregnancy test will be completed on Day 1 and negative test result must be confirmed prior to randomization.	
Serum FSH	х									Women of non-childbearing potential only. In the absence of 12 months of amenorrhea, confirmation with more than one FSH measurement is required.	
Blood Alcohol Test	Х										

	Screening]	Freatmen	t Period ^f			Follow -Up ^b	ET ^a	Notes
Visit	Screening	Week 0	Week 2	Week 4	Week 6	Week 8	Week 12	Week 16		
Study Day		Day 1	15	29	43	57	85	113		
Schedule Window (days)	-42 days		± 3	± 3	± 3	± 3	± 3	-7 /+2		Patients discontinuing the study at any time for any reason (Early Termination) should complete the ET visit as soon as feasible and return for a Follow-Up visit 4 weeks (-7 days /+2 days) after the last dose of study drug.
Study Drug Procedu	res									
Randomization		х								Confirm Inclusion and Exclusionary criteria before randomization and first dose of study drug.
Take Study Drug		x	x	x	x	x	х			At all study visits, study drug administration will be observed at the study site. Patients should be instructed to hold their dose of study drug on visit days until necessary visit procedures have been completed. On all other days, patients will self-administer the study drug orally once daily at approximately the same time, on an empty stomach (no food or drink besides clear liquids for approximately 2 hours before and 1 hour after study drug administration).
Dispense Study Drug ^h		х		х		X				Study drug will be assigned via the IWRS and provided in a carton containing four bottles: 2 capsules and 2 tablets for 4-week use.
Drug Accountability			х	х	х	х	х		х	

^a Patients discontinuing the study at any time for any reason (Early Termination) should complete the ET visit as soon as feasible and return for a Follow-Up 4 weeks (-7 days /+2 days) after the last dose of study drug.

^b The Follow-Up may take place at Week 16 (-7 days /+2 days) or 4 weeks (-7 days/+2 days) after the last dose of study drug if patients discontinue the study at any time for any reason (Early Termination).

^c Assessment should be collected pre-dose, as applicable.

^d A single PK sample should be collected between 2 and 6 hours postdose.

^eMRI-cT1 will be collected along with MRI-PDFF.

^f If a patient requires home quarantine due to SARS-CoV-2 infection or exposure, or due to COVID-19 symptoms or other associated concern with attending an inperson study visit, in accordance with Section 6.8.1 home health care visits may be made available to continue study assessments in the patient's home where feasible, and/or remote visits via telephone, telemedicine, or other appropriate virtual communication may be substituted for a visit to the site.

^g In the event of symptoms suggestive of COVID-19, ad hoc testing (including molecular test such as PCR or viral antigen serology, and/or antibody testing) may be completed at Investigator's discretion.

^h If a patient is required to be quarantined due to active infection of COVID-19 or exposure to COVID-19 or is otherwise unable to visit the site due COVID-19, study drug may be mailed to the patient or made available via another appropriate mechanism (ie, curbside pickup, etc.).

ⁱ If TE and CAP were collected at Screening, these assessments will not be required on Day 1. See Section 5.1, inclusion criteria #4b for additional details. ^j For patients participating in the PK/PD sub-study, drug must be self-administered in the morning approximately 24 hours before their Week 12 visit. If not, the Week 12 PK/PD sub-study visit should be re-scheduled for the following day.

Abbreviations: $7\alpha C4 = 7\alpha$ -hydroxy-4-cholesten-3-one; AE = adverse event; ALT = alanine transaminase; AST = aspartate transaminase; BMI = body mass index; CAP = controlled attenuation parameter; CK18 = cytokeratin-18; COVID-19 = coronavirus disease 2019; CTCAE = common terminology criteria for adverse events; sCTX = serum terminal telopeptide of type 1 collagen; ECG = electrocardiogram; ELF = enhanced liver fibrosis; ET = early termination; eGFR = estimated glomerular filtration rate; FSH = follicle stimulating hormone; HA = hyaluronic acid; FGF19 = fibroblast growth factor-19; HbA1c = hemoglobin A1c; HBsAG = hepatitis B surface antigen; HCV = hepatitis C virus; HIV = human immunodeficiency virus; hsCRP = high sensitivity C-reactive protein; INR = international normalized ratio; IWRS = interactive web response system; MRI-cT1 = magnetic resonance imaging corrected T1; MRI-PDFF = magnetic resonance imaging proton density fact fraction; NCI = National Cancer Institute; PCR = polymerase chain reaction; PD = pharmacodynamics; PIIINP = procollagen III N-terminal propeptide; sPINP = serum procollagen type I N-propeptide; PK = pharmacokinetics; PRO-C3 = released N-terminal pro-peptide of type III collagen; rT3 = reverse T3; SAE = serious adverse event; TBG = thyroid binding globulin; TE = transient elastography; TIMP-1 = tissue inhibitor of metalloproteinases-1; ULN = upper limit of normal; WOCBP = women of childbearing potential.

2. Introduction

